FeNO testing: The draft NICE asthma guideline recommends that FeNO testing should be considered in children with symptoms and under investigation for asthma who have normal spirometry and those with obstructive spirometry but no bronchodilator reversibility. FeNO testing in the diagnosis of asthma has been the topic of a separate NICE review published in April 2014, recommending FeNO testing as an option to diagnose asthma in children and adults with an intermediate probability of asthma in combination with other diagnostic options (12) There will be limited training requirements to perform the test and NICE have provided clear-cut guidelines for interpretation of the results.

Preliminary data/focus group meeting results:

Primary care practice focus group meeting: In preliminary work leading up to this protocol we conducted a focus group meeting with GPs, PN/HCAs and managers to explore attitudes, feasibility and potential barriers to implementation which have informed our implementation study proposal. Generally practice health care workers attitude towards spirometry and FeNO testing was favourable but training and capacity issues were raised as a major barrier to implementation.

One major finding from the focus group meetings was that the number of children aged 5-16 years on the asthma register appeared to be much lower than what would be predicted from epidemiological data. This data was gathered to understand how many children would need spirometry as part of their asthma review. Further inquiry of the practice database revealed that the number of children prescribed regular inhaled corticosteroids was more than double the number on the practice asthma register and when children were added who had been prescribed at least two short acting beta-2 agonist inhalers in the previous 12 months the total number of children rose to approximately 4-times the number on the asthma register and very close to the 10% of children predicted by epidemiological data.

These findings resulted from a small sample of children and may not be generalizable. Nonetheless, practice GPs felt that the 'cleaning up' of the asthma register by establishing the diagnosis or misdiagnosis of asthma would be a positive effect resulting from the objective tests recommended by NICE.

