7.2 Inclusion Criteria

Male or Female, aged 5-16 years who are:

1. On the practice asthma register or
2. Are prescribed regular (on repeat prescription) inhaled corticosteroids including beclometasone, fluticasone and budesonide and also search specifically for 'brands' that are commonly prescribed to include 'clenil', 'seretide', 'symbicort', and 'qvar' or
3. Have been prescribed ≥ 2 Salbutamol MDI's in the last 12 months or
4. Had a documented exacerbation of asthma in the last 12 months
5. Able and willing, in the opinion of the Investigator, to give informed consent

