8.3 Baseline Assessments

Health Care Workers’ Training Needs

The study team will gather information using site survey and readiness for change questionnaires at each participating practice. It is expected that practice GPs, nurses, HCAs and managers will complete these questionnaires.

The study team will seek the views particularly, but not exclusively, of the healthcare workers performing the objective tests (spirometry and FeNO) on the delivery and content of the training package and the training time available to those performing the tests.

Assessments Performed as Part of Recommended Standard Asthma Review

Asthma control test: We will use validated asthma control tests for children 4 to 11 years (7 questions) (17) and children 12 years and older (5 questions).

Check inhaler technique: Inhaler technique will be checked by the PN/HCA following training if required. An instruction sheet with written information and pictures will be given to the family.

Check prescription record: We will check and document the electronic prescribing record and dispensing record where available for asthma medication in the previous 6 months including the number of reliever and preventer inhalers. As part of the asthma review the practice PN/HCA will also check the prescription records and inform the GP if they have concerns regarding: suboptimal asthma control; where reliever and preventer medication use are unbalanced for example in cases where preventer prescribing is low and reliever prescriptions are high; and where there are concerns regarding adherence (i.e. fewer than expected number of inhalers dispensed).

Any child presenting to the review visit unwell or with poor lung function (FEV1 <75% predicted) will be referred to the practice GP for assessment.

Written personalised asthma action plan: All children will be given a written personalised asthma action plan. Where children already have an action plan this will be reviewed.

Spirometry and FeNO testing: Children will be asked to perform spirometry and a FeNO measurement where indicated.

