11. STATISTICS

11.1 Description of Statistical Methods

The qualitative data regarding opinions and barriers to implementation derived from change questionnaires conducted with the participating GP practices will be presented in report form. Appropriate non-parametric tests such as Kruskal-Wallis, Wilcoxon paired signed and Friedmans 2-Way ANOVA will be used to assess data; including the changes in number of children diagnosed with asthma, the number of misdiagnoses and alterations in prescribing (number of salbutamol inhalers/steroid courses) as a result of implementation of objective lung function tests. Paired t-tests or paired Wilcoxon signed rank tests will be used to assess the change in asthma control test scores, number of school days missed and number of carer work days missed.

A generalized linear mixed model with logit link function will also be used to compare the proportion of children with a personalised asthma plan and other secondary outcomes. The models will include important covariates such as age, gender and ethnicity, and the clustering effect of GP clinic will be accounted for. The effect of GP clinic will also be assessed by fitting a mixed effects model, GP clinic will be fitted as a random effect, covariates such as age, gender and ethnicity will be fitted as fixed effects.

All statistical analysis will be performed using R 3.2.0 (<http://www.r-project.org/>) and SPSS v22.

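### Some children enter because of recent salbutamol use or an exacerbation, so part of any before-after fall in prescribing is expected without an effect and should not be attributed to lung function testing

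*Combined protocol and SAP*

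**What the plan says.** Section 7.2 lists alternative routes of entry, and one is enough. Criterion 1 is "On the practice asthma register or" and criterion 2 is a repeat inhaled corticosteroid prescription. Criterion 3 reads "Have been prescribed ≥ 2 Salbutamol MDI's in the last 12 months or" and criterion 4 reads "Had a documented exacerbation of asthma in the last 12 months".

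The baseline looks back 6 months. Section 8.3 documents "asthma medication in the previous 6 months including the number of reliever and preventer inhalers", and section 8.2 records days of oral steroids over the same period. Follow-up is a record review 3-6 months after the visit (section 8.5). Section 8.4 states that nobody is randomised, and no comparison series is described.

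Section 11.1 says "Appropriate non-parametric tests such as Kruskal-Wallis, Wilcoxon paired signed and Friedmans 2-Way ANOVA will be used to assess data", and the data listed include "alterations in prescribing (number of salbutamol inhalers/steroid courses) as a result of implementation of objective lung function tests". The mixed models in the same section name age, gender, ethnicity and GP clinic. They do not name entry route or baseline use. Section 11.7 includes every participant.

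**The concern.** Criterion 3 puts a lower cut-off on one of the outcomes, the salbutamol count. Criterion 4 does the same to a correlate of the other, steroid courses. Counts fluctuate within a child. Children admitted because a count reached a cut-off will on average have a lower count next time, even if nothing has changed. A paired test without a comparison group cannot separate that fall from an effect, and equal before and after windows do not remove it.

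The causal wording adds a second problem. The same visit includes an inhaler technique check and a prescription and adherence check, and section 8.3 adds "All children will be given a written personalised asthma action plan". Even a genuine fall could not be assigned to spirometry and FeNO.

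At stake is the process-of-care result described in section 9.1, which supports the section 5.2 aim of showing the impact of implementation. An artefactual fall could be read as a benefit of testing.

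**Working it through.** **The plan's own figure.** The plan gives no prescribing rate, effect size or power. Its only related number is the planned 1000 children, which is a feasibility figure. Section 6.1 gives 1500-2000 eligible and a 50-70% response: 1500 × 0.5 = 750 up to 2000 × 0.7 = 1400. The planned 1000 lies inside this range and equals 2000 × 0.5.

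**Share entering on salbutamol alone.** Section 4 reports that children on regular inhaled steroids were more than double the register. When children with at least two reliever inhalers were added, "the total number of children rose to approximately 4-times the number on the asthma register". Set the register to 1.
- Register children all among the steroid users: (4 − 2)/4 = 50%.
- No overlap between the two groups: (4 − 2 − 1)/4 = 25%.

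Because the steroid group is *more than* double, each figure is a ceiling for its overlap assumption. Section 4 itself says the sample was small and may not generalise. Criterion 4 is ignored here.

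**Model (assumed).** Each child has a constant yearly rate drawn from a gamma distribution with mean m and shape k. Counts are Poisson, and the review has no effect. For a 12-month count x, the expected later yearly rate is (k + x)/(k/m + 1). Averaging over x ≥ 2 gives *before* = E[x | x ≥ 2] and *after* = (k + before)/(k/m + 1).

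For m = 2, k = 1: before = 4.00, after = (1 + 4)/(0.5 + 1) = 3.33, fall = 1 − 3.33/4.00 = 16.7%.

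For a pool with share s selected and the rest unselected at mean m, the fall is 1 − [s·after + (1 − s)·m]/[s·before + (1 − s)·m]. At m = 2, k = 1:
- s = 0.5: 1 − 2.667/3.000 = 11.1%.
- s = 0.25: 1 − 2.333/2.500 = 6.7%.

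| m per year | k | before | after | fall, selected | fall, pool 25% | fall, pool 50% |
|---|---|---|---|---|---|---|
| 1 | 0.5 | 3.51 | 2.67 | 23.8% | 12.8% | 18.5% |
| 1 | 1 | 3.00 | 2.00 | 33.3% | 16.7% | 25.0% |
| 1 | 2 | 2.71 | 1.57 | 42.1% | 20.0% | 30.8% |
| 2 | 0.5 | 4.87 | 4.30 | 11.8% | 5.3% | 8.4% |
| 2 | 1 | 4.00 | 3.33 | 16.7% | 6.7% | 11.1% |
| 2 | 2 | 3.50 | 2.75 | 21.4% | 7.9% | 13.6% |
| 3 | 0.5 | 6.17 | 5.72 | 7.3% | 3.0% | 4.9% |
| 3 | 1 | 5.00 | 4.50 | 10.0% | 3.6% | 6.3% |
| 3 | 2 | 4.33 | 3.80 | 12.3% | 4.0% | 7.3% |

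**Gap between search and review.** With a gap of g months (up to 6), only 6 − g months of the baseline lie inside the selection window. The baseline yearly rate becomes [(6 − g)·before + g·after]/6. At m = 2, k = 1, g = 3 it is (3 × 4.00 + 3 × 3.33)/6 = 3.67. The selected-group fall is then 1 − 3.33/3.67 = 9.1%, and the 50% pool falls 5.9%. At g = 6 or more the fall is zero.

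**Chance of a significant result.** I simulated 1000 children with no effect, no gap and 6 v 6 months, using a Wilcoxon signed-rank test at two-sided 5% (200 runs per scenario, means 1, 2 and 4). The test rejected in 9-93% of runs with 25% entering on salbutamol alone, and in 37-100% with 50%. In register and repeat-steroid children only, whatever their salbutamol count, it rejected in 1.5-7%.

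**Unequal windows.** With 6 v 3 months and raw counts, the test rejected in 100% of runs even in register and repeat-steroid children. Half the time gives half the count. This is a separate artefact, and splitting by entry route does not cure it.

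**Steroid courses.** If criterion 4 meant at least one course in 12 months, the selected-group fall would be 19-75% for assumed means of 1 down to 0.2 courses per year. An exacerbation is only a correlate of a course, so I carry no steroid figure into the conclusion.

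**The case against.** The strongest reply is that the overlap of windows is not established. Section 8.2 runs from search to letter to a family's phone call, and gives only a minimum of a week between receipt of the information sheet and the next clinic. Section 17 budgets 200 sessions over 60 weeks. If reviews trail the search by months, the artefact shrinks and then disappears. This stands: the figures at zero gap are the largest for each scenario, and the search and review dates need recording.

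Second, the size rests on assumed rates and a small preliminary sample. This also stands. At a 25% share and higher mean use, the pool fall is only a few per cent. Two inhalers in a year is a modest threshold, although any lower cut-off works in the same direction.

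Third, prescribing is neither one of the three numbered secondary objectives in section 5.2 nor an endpoint in section 6.2, and *implementation* could mean the whole package. That limits the weight of the point. It does not help section 11.1, which names objective lung function tests as what was implemented.

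A reader might also infer that register and repeat-steroid children give a clean estimate of the effect of testing. The documents do not support that. These children have no comparison group either, they may have been registered or put on repeat steroids after a bad spell, their families choose whether to book, and they receive the same bundled review.

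**Conclusion.** The concern holds in a limited form. Selection on salbutamol count and on exacerbations, a baseline that can fall inside the selection window, no comparison group and causal wording are all in the document. Part of any fall in prescribing is therefore expected without an effect, and none of it can be assigned to the tests alone.

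Under the stated gamma-Poisson assumptions, with equal windows and no gap, the salbutamol fall is 7-42% in children selected on at least 2 inhalers and 3-31% in the whole pool for a 25-50% share. A 3-month gap roughly halves it (17% to 9% at mean 2, shape 1), and a gap of 6 months or more removes it.

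A reader might infer that a significant fall is bound to be false, or that the study as a whole is compromised. Neither follows. The rejection rate ranges from 9% to 100% over the assumptions, most or about half of the children enter by other routes, and the primary objective on training and capacity does not depend on this comparison.

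**What to change.** - On the CRF, record which of criteria 1-4 each child meets, with the search and review dates. Check criterion 4 from the consented record, because the search in section 8.2 covers only register and medication.
- In section 11.1, express salbutamol and steroid prescribing as rates per month, over equal windows where possible.
- Report the change separately for (a) all children meeting criterion 1 or 2, whether or not they also meet 3 or 4, as the main estimate and the one less affected by selection, and (b) children eligible only through 3 or 4, labelled as expected to fall by selection. Group (a) must keep children who also meet 3 or 4, since dropping them would select for low use.
- Replace the attributing phrase in section 11.1 with *after the asthma review including objective tests*, and attribute no change in either group to the tests alone.

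Cost: a few CRF fields, a record check for criterion 4, and changes to the analysis wording. The main estimate rests on about half to three quarters of the children (1 − 0.50 to 1 − 0.25), and the claim is more modest.

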8. STUDY PROCEDURES

8.1 Informed Consent

Children aged 5 to 16 years who fulfil the inclusion criteria will be identified from electronic searches performed by the practice staff for the purposes of inviting them for an asthma review. We will provide the practices with patient information sheets (PIS) to post out with the invitation letters sent out by the GPs themselves. The PIS will detail no less than: the exact nature of the study and that the parent is free to withdraw the participant from the study at any time for any reason without prejudice to future care, and that there is no obligation to give consent for access to their child's records in the first place. Even if the parent does not consent to the study, their child is still welcome to the full asthma review including lung function tests as these are part of recommended standard care.

On the day of the clinic, a member of the research team will talk to the family prior to their appointment and explain the study and to answer any questions. The participant will be allowed as much time as wished to consider the information, and the opportunity to question the study team to decide whether they will participate in the study.

It will be made clear that none of the tests performed in the asthma clinic, except the short health economic questionnaires, are part of the research and should be viewed as best practice. We are only seeking consent to: 1) access their child's electronic records in order to obtain information including recent exacerbations and medications prescribed, 2) record answers to a health economic questionnaires onto the CRF, 3) time how long it takes to perform each lung function test and 4) ask their GPs to contact them in 3-6 months' time by post to complete a follow up health economic questionnaire and ACT. Written consent will then be taken from the parents should they agree to participate.

The person who obtains the consent will be suitably qualified and experienced, and have been authorised to do so by the Chief Investigator as detailed on the Delegation of Authority and Signature log for the study. The original signed form will be retained at the study site within Investigator Site File (ISF). A copy of the signed Informed Consent will be given to participants and a copy retained in the participant medical notes. Anyone not medically qualified will undergo UHL consent training.

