8.4 Randomisation and Codebreaking

There is no randomisation of participants in this study.

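### Section 11.1 credits prescribing changes to the lung function tests, but the same visit also delivers an inhaler check, an action plan and a prescription check with GP alert

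*Combined protocol and SAP*

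**What the plan says.** Section 11.1 lists the data to be assessed with non-parametric tests, "including the changes in number of children diagnosed with asthma, the number of misdiagnoses". The same sentence then turns to prescribing: "alterations in prescribing (number of salbutamol inhalers/steroid courses) as a result of implementation of objective lung function tests". The causal phrase at the end covers diagnosis, misdiagnosis and prescribing. The next sentence, on asthma control scores and days missed from school or work, speaks only of assessing change.

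Section 8.3 describes what happens at the review besides spirometry and FeNO:

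- Inhaler technique: "Inhaler technique will be checked by the PN/HCA following training if required". The family also gets an instruction sheet.
- Action plan: "All children will be given a written personalised asthma action plan".
- Prescriptions: the practice nurse or healthcare assistant is to "check the prescription records and inform the GP if they have concerns regarding: suboptimal asthma control". Unbalanced reliever and preventer use and doubtful adherence also go to the GP.

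On comparators, section 8.4 states: "There is no randomisation of participants in this study". Section 8.1 says of families who decline consent that "their child is still welcome to the full asthma review including lung function tests".

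Section 9.1 (impact on processes of care) has the team look in the records for prescribing changes and for whether a diagnosis changed because objective tests were available. It does not ask for the reason behind a prescribing change.

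**The concern.** Salbutamol and steroid prescribing can move for reasons unrelated to a spirometry or FeNO result. The prescription check with GP alert acts directly on the outcome being tested, and better technique or an action plan can alter reliever and steroid use. Anyone following section 11.1 as written would report the combined effect of an asthma review as the effect of the tests. This would happen even with complete data and no selection problem, because the fault lies in what the comparison contains.

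At stake is the stated impact of testing on care, which belongs to the secondary objectives in section 5.2. A report that testing changed prescribing would tell practices something this design cannot show.

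**Working it through.** **The plan's own figure.** Section 6.1 gives 1500 to 2000 eligible children and a response rate of 50-70%. 1500 × 0.50 = 750; 1500 × 0.70 = 1050; 2000 × 0.50 = 1000; 2000 × 0.70 = 1400. The planned 1000 lies in this range. It is a recruitment figure: section 11.2 gives no power calculation, effect size or SD. It is used below only as n.

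**Is there any contrast that isolates the tests?** Taking each possible source in turn:

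1. *Allocation.* None (section 8.4). The comparison is each child before and after the review.
2. *Families who decline consent.* They are offered the same review with the same tests (section 8.1), and consent is what opens the records, so they cannot serve as an untested group.
3. *Children who cannot do the tests.* They are excluded (section 7.3).
4. *Covariates.* Section 11.1 names age, gender, ethnicity and GP clinic. None distinguishes the tests from the other parts of the visit.
5. *Reason for change.* Section 9.1 seeks this for diagnosis only.

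The tests do have a route to prescribing, for example through GP referral of children with poor lung function (section 8.3). The difficulty is that this route runs alongside the others and nothing planned separates them.

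**How easily could the other components alone give a significant result?** This is an illustration. The effects are assumed, the test is taken as two-sided at 5% (section 11.3 does not state sidedness), children are treated as independent, and a normal approximation to a paired test stands in for the signed-rank test.

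P(significant) = Φ(d√n − 1.96) + Φ(−d√n − 1.96), where d is the shift due to the non-test components in SDs of the change, and the tests contribute zero.

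| d | n = 1000 | n = 500 |
|---|---|---|
| 0.05 | d√n = 1.58; 35% | d√n = 1.12; 20% |
| 0.10 | d√n = 3.16; 89% | d√n = 2.24; 61% |
| 0.15 | d√n = 4.74; 99.7% | d√n = 3.35; 92% |

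The shift detectable with 80% power at n = 1000 is (1.960 + 0.842)/√1000 = 0.089 SD. Quite small effects of the ordinary review would therefore often be significant and, under the present wording, be credited to the tests.

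**Why even the whole review should be described with care.** Children may enter on recent salbutamol prescribing or a recent exacerbation (section 7.2), which invites regression to the mean. The look-back is 6 months (sections 8.2 and 8.3) and the follow-up 3 to 6 months (section 8.5). At a constant rate, raw counts would stand in a ratio of 3/6 = 0.50 to 6/6 = 1.00. These are separate issues, but they favour neutral wording such as 'following'.

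**The case against.** The best reply is that the whole review is the intervention. Section 5.2 frames the secondary objectives as the impact of implementing the guidelines, and section 14.1 says every aspect of the review is recommended nationally. On that reading the phrase in section 11.1 is loose wording. This has force, and it points to the remedy: bring section 11.1 into line with section 5.2. It does not remove the point, because section 6.1 also gives the impact of implementing lung function testing as the reason for consenting children. The test-specific claim is thus made in more than one place.

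A second reply is that the rationale in section 4 says the study does not ask whether the tests should be used, only how, and that the primary objective is training and capacity. Running costs are to come from test timing and patients per session (section 9.1). This stands. A reader might infer that the prescribing result would mislead a decision to fund the tests, but the documents plan no such decision on prescribing counts. It limits the severity.

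A third reply concerns the reason-for-change item: GP notes may not state a reason, and mixed reasons need a rule. That is fair, and the item should be reported as description only.

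**Conclusion.** The point holds for prescribing. Section 11.1 makes a test-specific causal claim that a single-group before-after comparison of a multi-part review cannot support. The conclusion rests on the text alone. The percentages above are illustrative, and the documents give nothing from which to size the actual misattribution.

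Stronger readings are not supported:

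- *Diagnosis changes are equally unattributable.* Section 5.2 defines the diagnostic outcomes by the tests, section 8.3 makes test thresholds part of the diagnosis, and section 9.1 already seeks whether a diagnosis changed because of them. An inhaler check or action plan has no evident route to a diagnostic label. Some uncertainty remains, since the clinical history and the prescription check could prompt a rethink, but diagnosis is largely unaffected.
- *Asthma control scores and days missed are misattributed too.* Section 11.1 does not ascribe them to the tests.
- *The case report form fails to separate reasons for change.* The form is not in the documents. One can say only that the protocol plans no such item for prescribing.
- *No child is reviewed without tests.* Section 8.3 also says that the tests are done where indicated, so a few untested children are possible. They are not planned as a comparator.
- *Comparing children by test result would recover the effect.* Those groups may differ in severity and control, so the comparison is confounded.

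Severity is moderate: prescribing is a secondary outcome in a study whose main aim is training and capacity.

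**What to change.** 1. In section 11.1, and later in the conclusions, describe prescribing changes as changes following a guideline-based asthma review that included lung function tests. This matches section 5.2.
2. Extend the record review in section 9.1. For each prescribing change, where the notes state a reason, mark it as prompted by a test result, by another component of the review, or mixed/unclear. Fix the rule for mixed reasons beforehand, and report the shares descriptively.
3. If changes are also broken down by test result, label the breakdown descriptive and confounded by severity and control.

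The cost is a wording change, some extra abstraction at a record review already planned, a number of unclear entries, and a weaker causal statement. A test-specific effect on prescribing would need a group reviewed without tests, which this study does not plan and does not need for its primary objective.
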